The adult AS and PsA secukinumab data support the proposed secukinumab study in children with similar pediatric spondyloarthritic conditions: ERA and JPsA. This study will investigate secukinumab treatment in children \geq 2 to $<$ 18 years of age with active JPsA or ERA JIA using a pediatric dose equivalent to the adult 150mg dose. To ensure children with a more SpA-like condition ([Martini 2012](#)) are not excluded, the ILAR diagnostic criteria for JPsA are modified NOT to exclude those who are:

- HLA-B27-positive male beginning after the 6th birthday;
- those who have AS, ERA, sacroiliitis with Inflammatory Bowel Disease (IBD), reactive arthritis (Reiter's syndrome), or acute anterior uveitis, or a history of one of these disorders in a first-degree relative.

This 2-year study consists of 3 parts plus a post-treatment follow-up period: The initial Treatment Period 1 will entail open-label secukinumab administered subcutaneously every week for the first 4 weeks (loading dose period) and at Week 8. Responders (minimum JIA ACR30 response) at the end of Treatment Period 1 (Week 12) will enter into Treatment Period 2 and be randomized 1:1 at Week 12 to either continue secukinumab or begin placebo in a blinded fashion every 4 weeks. Non-responders will not be dosed and will undergo an end of study visit on the same day and enter the Post-treatment follow-up period. Treatment Period 2 will continue until 33 patients experience a disease flare (as per American College of Rheumatology (ACR) flare definition). Patients experiencing a flare and those who remain (in

Treatment Period 1 or 2) when Treatment Period 2 completes will enter Treatment Period 3 to receive open-label secukinumab every 4 weeks until week 100. A total study duration of 104 weeks at the patient level is reached. A Post-treatment follow-up visit is performed 12 weeks after last study treatment administration for all patients unless the patient enters the extension trial.

All patients who successfully complete the study (104 weeks) will be eligible to continue secukinumab treatment in an extension trial.

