3.1 Study design

This is a double-blind, placebo-controlled, event-driven randomized withdrawal study to investigate the efficacy and safety of secukinumab treatment in the JIA categories of JPsA and ERA. The study is divided into 3 parts (plus a post-treatment follow-up period) consisting of open-label, single-arm active treatment in Treatment Periods 1 and 3 and a randomized, double-blind, placebo controlled, event-driven withdrawal design in Treatment Period 2, as described below:

Treatment Period 1: A maximum 8-week screening period is used to assess patient eligibility. All eligible patients will enter Treatment Period 1 to receive 12-weeks of open-label secukinumab at a dose predicted to achieve secukinumab serum levels equivalent to adults administered a 150 mg dose regimen (see [Section 3.3](#) for details). Secukinumab will be administered subcutaneously (s.c.) weekly for the first 4 weeks (Baseline, Weeks 1, 2, 3, 4) and then every 4 weeks thereafter. Clinical response (JIA ACR 30) will be assessed at Week 12. Responders will advance to Treatment Period 2 and non-responders must exit the trial (early termination visit and enter into the Post-treatment follow-up period).

Treatment Period 2: Patients with a clinical response (JIA ACR30) at Week 12 will enter double-blind withdrawal Treatment Period 2 to be randomized 1:1 to either secukinumab or placebo on that visit. Treatment Period 2 is event driven and will close when 33 patients experience a disease flare as per JIA definition ([Appendix 8](#)). If Treatment Period 2 is closed when a patient becomes eligible to enter Treatment Period 2, the patient will skip Treatment Period 2 and advance directly to Treatment Period 3. When the 33rd flare is observed, all investigators will be informed that Treatment Period 2 is closed and all remaining patients will enter Treatment Period 3 at their next scheduled visit. Because Treatment Period 2 is event driven, it is possible that a patient remains in Treatment Period 2 for the duration of the study (Week 104) before 33 disease flares are observed. Such patients will complete the study without having entered Treatment Period 3.

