Treatment Period 3: Patients experiencing a disease flare in Treatment Period 2 will immediately enter Treatment Period 3 to receive open label secukinumab every 4 weeks until total study duration of 104 weeks for that patient is achieved. Additionally, when Treatment Period 2 closes, all remaining patients in Treatment Period 2 will enter Treatment Period 3 at their next scheduled visit and all remaining Treatment Period 1 patients who become eligible to enter Treatment Period 2 will skip Treatment Period 2 and enter Treatment Period 3 directly. Consequently, the starting time point of Treatment Period 3 for each patient may be different.

Post-treatment follow-up: All patients completing the study (Week 104) or who discontinue early will enter the Post-treatment follow-up period lasting 12 weeks from the last study drug dose administration. Only patients who qualify and enter the secukinumab extension trial without interruption of secukinumab treatment will not require this Post-treatment follow-up visit.

Due to the event driven design of Treatment Period 2, the lengths of Treatment Periods 2 and 3 will be variable and patient-specific. Based on the study design, a patient may participate in:

1. **Treatment Period 1 only** if the patient is a non-responder at the end of Treatment Period 1 and must discontinue from the study.
2. **Treatment Periods 1, 2, and 3.**
3. **Treatment Periods 1 and 2 only** if the patient never experiences a disease flare after randomization into Treatment Period 2 and reaches a total study duration of 104 weeks before a total 33 flares in Treatment Period 2 are observed.
4. **Treatment Periods 1 and 3 only** if 33 flares are observed in Treatment Period 2 prior to or at the time the patient reaches Week12 (end of Treatment Period 1) and is eligible to enter Treatment Period 2. In this situation, the patient will enter Treatment Period 3 directly from Treatment Period 1 to receive open-label secukinumab.

All patients will participate in the Post-treatment follow up period, except for those entering the extension study.

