- **Treatment Period 2 treatment withdrawal:** Patients who are a responder (minimum JIA ACR30) at the end of Treatment Period 1 visit at Week 12, will move directly into Treatment Period 2 *at that same visit* to be randomized 1:1 to receive blinded secukinumab (75mg for < 50kg [0.5 mL PFS] or 150 mg for \geq 50 kg [1mL PFS] or matching placebo administered in Treatment Period 2 and then every four weeks until either experiencing a disease flare or completion of Treatment Period 2 (33 disease flares observed in the overall study population). For patients who are eligible to enter Treatment Period 2, but it has closed (because 33 disease flares were observed), they will skip Treatment Period 2 and enter directly into Treatment Period 3 *at that visit* to begin open-label secukinumab administration.

- Treatment Period 3 open-label: Secukinumab 75 mg (< 50 kg, 0.5 mL PFS) or 150 mg (\geq 50 kg, 1mL PFS) s.c will be administered every 4 weeks until Week 100 included.

Figure 3-1 **Study design**

The time point for entering Treatment Period 3 will be either when the patient experiences a disease flare, or on/after the completion of Treatment Period 2. Consequently, the duration in Treatment Period 2 will be up to 92 weeks for patients without a disease flare if Treatment Period 2 does not close before the patient reaches 104 weeks of total study participation. Patients could enter Treatment Period 3 at any point from Week 12 to Week 104.

All patients completing the Week 104 visit or who discontinue early will have a Post-treatment follow-up visit 12 weeks from the last study drug dose. Only patients who enter the extension trial without interruption of their secukinumab treatment will not require this Post-treatment follow-up visit.

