5.6 Study Completion and Discontinuation

5.6.1 Study completion and post-study treatment

A patient will be considered to have completed the study when the patient has received a maximum of 104 weeks of study treatment and completed all of the scheduled study assessment and procedures up to and including the Week 112 visit. All patients who complete the scheduled study assessments and procedures up to and including Week 104 will be eligible to enter an extension trial to continue secukinumab treatment without interruption. Patients who enter the extension study will be considered study completers at Week 104 and the follow-up visit at Week 112 will not be performed.

Information on the subject's completion or premature discontinuation of the study and the reason for discontinuation of the study will be recorded on the appropriate eCRFpage. Additionally, the investigator or site staff must contact the IRT as soon as possible to record the subject's study completion and/or discontinuation.

The Investigator must provide follow-up medical care for all subjects who are prematurely withdrawn from the study, or must refer them for appropriate ongoing care. This care may include initiating another treatment outside of the study as deemed appropriate by the investigator. This treatment may be any non-biologic DMARD. In case of a biologic treatment, a waiting period of 3 months before initiating the treatment is recommended.

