9.6 Sample size calculation

It is assumed that the Flare-free time follows an exponential distribution with a constant hazard ratio.

The hazard ratio of flare events for the secukinumab group relative to placebo group is estimated to be 0.32 in Treatment Period 2. The hazard ratio of 0.32 was used to establish the sample size necessary in Treatment Period 2 and consequently Treatment Period 1 (derived from the median time to disease flare for ETANERCEPT and placebo in LOVELL et. al. 2000). With the hazard ratio assumed to be 0.32, 33 flares are necessary to detect a statistically significant difference between secukinumab and placebo assuming 90% power and a 1-sided significance level of 0.025. No data is available to estimate the placebo hazard rate beyond 6-months. Given that uncertainty and a maximum 21-month follow-up in Treatment Period 2, the total sample size necessary to achieve 33 flares in Treatment Period 2

is estimated to be at least 60 and at most 80 patients. Assuming approximately 70% to 85% of patients respond in Treatment Period 1, the estimated minimum number of patients treated in Treatment Period 1 is between 70 and 86. Under the assumption of 12 months of accrual duration, the total maximum expected study duration is 33 months. The expected number of flare events is 12 and 21 respectively for secukinumab and placebo group in Treatment Period 2.

10 Ethical considerations

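### Is the 33-month total study duration in Section 9.6 too short because it leaves out Treatment Period 1?

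*Protocol*

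**What the plan says.** The sample size paragraph (Protocol, Section 9.6) sets "a maximum 21-month follow-up in Treatment Period 2", then continues "Under the assumption of 12 months of accrual duration" and concludes that "the total maximum expected study duration is 33 months". The sentence after that gives the expected number of flares per arm in Treatment Period 2.

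Other sections describe time on study for a single patient. Section 3.1 says that "the duration in Treatment Period 2 will be up to 92 weeks for patients without a disease flare", if the period has not closed earlier. It also describes a patient who never flares and "reaches a total study duration of 104 weeks before a total 33 flares in Treatment Period 2 are observed". Section 1.1 says: "A total study duration of 104 weeks at the patient level is reached". Section 5.6.1 adds a Week 112 visit for patients who do not enter the extension; for those who do, "the follow-up visit at Week 112 will not be performed".

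**The concern.** A figure called the total maximum should bound the whole trial, and 33 months does not. Every patient spends 12 weeks in Treatment Period 1 before randomization, and where the protocol speaks of a patient's total study duration it counts those weeks. A last-enrolled patient who completes as scheduled would still be on study after month 33.

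Early closure of Treatment Period 2 does not rescue the figure. Patients remaining at closure move to open-label Treatment Period 3 and continue to Week 104, so an early 33rd flare does not bring the last visit forward.

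If ethics committees, sites or drug supply planning took the number as the length of the trial, they would be about three months short.

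**Working it through.** **Inputs (all from the protocol)**
- Accrual: 12 months (Section 9.6).
- Maximum Treatment Period 2: 21 months (Section 9.6), or 92 weeks (Section 3.1).
- Treatment Period 1: 12 weeks (Section 3.1).
- Total per patient: 104 weeks (Sections 1.1 and 3.1).
- Follow-up visit: Week 112, if no extension (Section 5.6.1).
- Screening: up to 8 weeks (Section 3.1).

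**Conversion.** Months = weeks × 7 / 30.44. This gives 8 weeks = 1.84, 12 weeks = 2.76, 92 weeks = 21.16, 104 weeks = 23.92 and 112 weeks = 25.76 months.

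**Reproducing the stated figure.** 12 + 21 = 33 months exactly; with 92 weeks, 12 + 21.16 = 33.2. The number is accrual plus the longest possible Treatment Period 2.

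**Whole-trial totals under different start and end points**

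| Span | Sum | Months |
|---|---|---|
| First randomization to latest end of Treatment Period 2 | 12 + 21.16 | 33.2 |
| First baseline to last Week 104 | 12 + 23.92 | 35.9 |
| First baseline to last Week 112 | 12 + 25.76 | 37.8 |
| First screening to last Week 112 | 1.84 + 12 + 25.76 | 39.6 |

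**Does the meaning of accrual matter?** If the 12 months count randomizations, the first patient's Treatment Period 1 comes before them: 2.76 + 12 + 21.16 = 35.9. From first baseline to last Week 104, both readings give about 36 months, so 33 is short by 35.9 − 33 = 2.9 months, or 37.8 − 33 = 4.8 months to Week 112.

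**Does anything depend on it?** The event target needs only the hazard ratio, the significance level and the power: 4 × (1.960 + 1.282)² / (ln 0.32)² = 42.03 / 1.298 = 32.4, rounded up to 33 flares. Duration does not enter. The 21-month follow-up behind the 60 to 80 patients is stated separately and agrees with the 92 weeks. No other section of the protocol uses 33 months. Section 3.1 closes Treatment Period 2 on the 33rd flare, and patients finish by study week.

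**The case for a change.** The strongest case for a change is that the protocol contradicts its own schedule in plain, current text. Section 9.6 says total, names Treatment Period 2 explicitly only for the 21-month follow-up, and does not restrict the 33 months to that period. Neither reading of accrual nor early closure makes 33 an upper bound on the trial, and the correction would take one line.

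Most of this stands. Read literally, the label claims more than the number delivers. Three things weaken it as a reason to act.

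- Accrual plus maximum follow-up of randomized patients is the usual duration in an event-driven calculation, and the neighbouring sentences concern Treatment Period 2. Section 9.4.1 uses the word study in the same narrow way: it tests the hypothesis once the flares are observed and the study has stopped, although only Treatment Period 2 has stopped by then.
- The 104 weeks is a per-patient duration, not the calendar length of the trial, so the two statements describe different quantities.
- About 36 months is no more definitive as a total. It leaves out screening, the Week 112 visit and any delay from the enrollment holds for the pharmacokinetic interim analysis that the 12 months of accrual do not absorb.

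**Conclusion.** The observation is correct, but it is clerical. The 33 months is right for the span from first randomization to the latest possible end of Treatment Period 2, and loosely labelled as the total for the study. As a whole-trial figure it would be about 2.9 months short of the last patient's Week 104 and about 4.8 months short of the last Week 112. These sizes assume that the 12 months of accrual hold and exclude screening.

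No change follows because nothing is gained. The hazard ratio, the 33 flares, the power, the logrank test, the closing rule for Treatment Period 2 and the visit schedule are the same whichever number is printed. Anyone planning the calendar can add accrual to the 104 weeks per patient, both of which the protocol states.

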10.1 Regulatory and ethical compliance

This clinical study was designed and shall be implemented, executed and reported in accordance with the ICH Harmonized Tripartite Guidelines for Good Clinical Practice, with applicable local regulations (including European Directive 2001/20/EC, US CFR 21, and Japanese Ministry of Health, Labor, and Welfare), and with the ethical principles laid down in the Declaration of Helsinki.

10.2 Informed consent procedures

Eligible patients may only be included in the study after providing written (witnessed, where required by law or regulation), Institutional Review Board (IRB)/ Independent Ethics Committee (IEC)-approved informed consent, or, if incapable of doing so, after such consent has been provided by a legally acceptable representative(s) of the patient. In cases where the patient's representative gives consent, the patient must be informed about the study to the extent possible given his/her understanding. If the patient is capable of doing so, he/she must indicate assent by personally signing and dating the written informed consent document or a separate assent form. Informed consent must be obtained before conducting any study-specific procedures (e.g. all of the procedures described in the protocol). The process of obtaining informed consent must be documented in the patient source documents.

Novartis will provide to investigators in a separate document a proposed informed consent form that complies with the ICH GCP guideline and regulatory requirements and is considered appropriate for this study. Any changes to the proposed consent form suggested by the Investigator must be agreed to by Novartis before submission to the IRB/IEC, and a copy of the approved version must be provided to the Novartis monitor after IRB/IEC approval.

In pediatric patients (< 18 years of age) parental permission and, whenever possible, child assent is needed instead of the procedure for informed consent used for research involving adults. In general, one or both parents or a guardian must be provided with the information ordinarily required for informed consent, so that they may decide whether to allow the child to participate, and children capable of assent must also express their willingness to participate. These forms will be submitted for IRB/IEC/REB approval.

Women of child bearing potential/guardian must be informed that taking the study treatment may involve unknown risks to the fetus if pregnancy were to occur during the study and agree that in order to participate in the study they must adhere to the contraception requirement for the duration of the study. If there is any question that the patient will not reliably comply, they must not be entered in the study.

10.3 Responsibilities of the Investigator and IRB/IEC

Before initiating a trial, the Investigator/institution must obtain approval/favorable opinion from the Institutional Review Board/Independent Ethics Committee (IRB/IEC) for the trial protocol, written informed consent form, consent form updates, subject recruitment procedures (e.g., advertisements) and any other written information to be provided to patients/guardians. Prior to study start, the Investigator is required to sign a protocol signature page confirming his/her agreement to conduct the study in accordance with these documents and all of the instructions and procedures found in this protocol and to give access to all relevant data and records to Novartis monitors, auditors, Novartis Quality Assurance representatives, designated agents of Novartis, IRBs/IECs, and regulatory authorities as required. If an inspection of the clinical site is requested by a regulatory authority, the Investigator must inform Novartis immediately that this request has been made.

10.4 Publication of study protocol and results

The key design elements of this protocol will be posted in a publicly accessible database such as clinicaltrials.gov. In addition, upon study completion and finalization of the study report the results of this trial will be either submitted for publication and/or posted in a publicly accessible database of clinical trial results.

11 Protocol adherence

This protocol defines the study objectives, the study procedures and the data to be collected on study participants. Additional assessments required to ensure safety of patients/subjects should be administered as deemed necessary on a case by case basis. Under no circumstances is an Investigator allowed to collect additional data or conduct any additional procedures for any research related purpose involving any investigational drugs under the protocol.

Investigators ascertain they will apply due diligence to avoid protocol deviations. If an Investigator feels a protocol deviation would improve the conduct of the study this must be considered a protocol amendment, and unless such an amendment is agreed upon by Novartis and approved by the IRB/IEC and health authorities, where required, it cannot be implemented.

The following defined notable laboratory or vital sign abnormalities, except creatinine clearance, will be communicated at the same time as they are sent to investigators to Novartis. Novartis will determine if further consultations with Investigator(s) are appropriate.

Laboratory Criteria

Newly occurring selected notable laboratory abnormalities in pediatric patients at the time of the assessment:

Biochemistry

- Alanine aminotransferase (ALT)(SGPT):
 - > Upper Limit of Normal (ULN)
 - $\geq 3 \times$ ULN
 - $\geq 5 \times$ ULN
 - $\geq 8 \times$ ULN
 - $\geq 10 \times$ ULN
- Aspartate aminotransferase (AST) (SGOT):
 - >ULN
 - $\geq 3 \times$ ULN
 - $\geq 5 \times$ ULN
 - $\geq 8 \times$ ULN
 - $\geq 10 \times$ ULN
- Total Bilirubin (TBL)
 - >ULN,
 - $\geq 1.5 \times$ ULN,
 - $\geq 2 \times$ ULN
- ALP
 - >ULN
 - $\geq 1.5 \times$ ULN,
 - $\geq 2 \times$ ULN,
 - $\geq 3 \times$ ULN
 - $\geq 5 \times$ ULN
- ALT and/or AST $>3 \times$ -, $5 \times$ -, $10 \times$ ULN accompanied by TBL $>2 \times$ ULN
- ALT or AST $>3 \times$ ULN and TBL $>2 \times$ -, and ALP $>2 \times$ ULN.
- ALP $>3 \times$ ULN and TBL $>2 \times$ ULN

- Gamma-Glutamyltransferase (GGT):
 - >ULN
 - $\geq 3 \times \text{ULN}$
 - $\geq 5 \times \text{ULN}$
- Creatinine (serum): $\geq 1.5 \times \text{ULN}$
- Creatinine clearance (Schwartz formula[§]): $\geq 25\%$ decrease from baseline, ≥ 3 months in duration
- Protein urine dipstick:
New protein $\geq 1+$, ≥ 3 months in duration
- Creatinine clearance (Schwartz formula[§]): $\geq 25\%$ decrease from baseline, ≥ 3 months in duration in combination with protein urine dipstick resulting in new protein $\geq 1+$, ≥ 3 months in duration
- Total Cholesterol: $\geq 1.5 \times \text{ULN}$
- Triglycerides: $\geq 5.7 \text{ mmol/L}$.

[§]Schwartz formula- Creatinine clearance (mL/min/1.73m²) was derived using the following formula $0.413 \times \text{length (cm)} / (\text{serum creatinine (mg/dL})$ ([Schwartz et al 2009](#)).

For creatinine clearance only, baseline value for the decrease from baseline criterion will be calculated as the average of all values prior to the first dose (i.e. screening and baseline values).

Hematology

- Hemoglobin: $\geq 20 \text{ g/L}$ decrease from baseline,
or $< 85 \text{ g/L}$ for < 16 years of age
 $< 100 \text{ g/L}$ for ≥ 16 years of age
- Absolute neutrophils:
 - Grade 1: $< \text{LLN} - 1.5 \times 10\text{E}9/\text{L}$
 - Grade 2: $< 1.5 - 1.0 \times 10\text{E}9/\text{L}$
 - Grade 3: $< 1.0 - 0.5 \times 10\text{E}9/\text{L}$
 - Grade 4: $< 0.5 \times 10\text{E}9/\text{L}$
- Criteria based on CTC grades for platelet count:
 - Grade 1: $< \text{LLN} - 75.0 \times 10\text{E}9/\text{L}$
 - Grade 2: $< 75.0 - 50.0 \times 10\text{E}9/\text{L}$
 - Grade 3: $< 50.0 - 25.0 \times 10\text{E}9/\text{L}$
 - Grade 4: $< 25.0 \times 10\text{E}9/\text{L}$
- Criteria based on CTC grades for WBC:
 - Grade 1: $< \text{LLN} - 3.0 \times 10\text{E}9/\text{L}$
 - Grade 2: $< 3.0 - 2.0 \times 10\text{E}9/\text{L}$
 - Grade 3: $< 2.0 - 1.0 \times 10\text{E}9/\text{L}$
 - Grade 4: $< 1.0 \times 10\text{E}9/\text{L}$
- Absolute Lymphocytes: $< \text{LLN}$

- Absolute Eosinophils: $\geq 1.1 \times \text{ULN}$
- Absolute Eosinophils: $\geq 0.45 \times 10^9/\text{L}$

Vital Signs

The following criteria will be used.

Note: The age is the age at the time of the visit.

Systolic blood pressure (mmHg):

- High: $>\text{ULN}$ and Increased >20 in change from baseline

Diastolic blood pressure (mmHg):

- High: $>\text{ULN}$ and Increased >20 in change from baseline

Pulse (bpm)[§]:

- High: $>\text{ULN}$ and Increased >20 in change from baseline
- Low: $<\text{LLN}$ and Decreased >20 in change from baseline

Note: Only post-baseline values will be flagged as notable abnormalities

Table 13-1 Reference ranges for systolic and diastolic blood pressures and pulse.

Age	Systolic Blood Pressure lower and upper limits (mmHg)	Diastolic Blood pressure lower and upper limits (mmHg)	Pulse lower and upper limits (Beats per minute)
2 yrs	84-117	39-72	90-150
3 yrs	86-120	44-76	90-150
4 yrs	88-122	47-79	90-150
5 yrs	89-123	50-82	65-135
6 yrs	91-125	53-84	65-135
7 yrs	92-126	55-86	60-130
8 yrs	94-127	56-88	60-130
9 yrs	95-129	57-89	60-130
10 yrs	97-130	58-90	60-110
11 yrs	99-132	59-90	60-110
12 yrs	101-135	59-91	60-110
13 yrs	104-137	60-91	60-110
14 yrs	106-140	60-92	60-110
15 yrs	107-142	61-93	60-110
16 yrs	108-145	63-94	60-110
17 yrs	108-147	64-97	60-110
18 yrs	108-147	64-97	60-100

Table 13-2 Recommended dimensions for blood pressure cuff bladders

	Width [cm]	Length [cm]	Maximum Arm Circumference [cm]*
Newborn	4	8	10
Infant	6	12	15
Child	9	18	22
Small adult	10	24	26
Adult	13	30	34
Large adult	16	38	44

*calculated so that the bladder can encircle even the largest arm by at least 80%

Source: [Feld LG and Corey H \(2007\)](#): Hypertension in childhood, Pediatric in Review 28: 283-98

14 Appendix 2: Liver event and Laboratory trigger Definitions and Follow-up Requirements

Table 14-1 Liver Event and Laboratory Trigger Definitions

	Definition/threshold
LIVER LABORATORY TRIGGERS	
 • $3 \times \text{ULN} < \text{ALT} / \text{AST} \leq 5 \times \text{ULN}$ • $1.5 \times \text{ULN} < \text{TBL} \leq 2 \times \text{ULN}$
LIVER EVENTS	
 • $\text{ALT or AST} > 5 \times \text{ULN}$ • $\text{ALP} > 2 \times \text{ULN}$ (in the absence of known bone pathology) • $\text{TBL} > 2 \times \text{ULN}$ (in the absence of known Gilbert syndrome) • $\text{ALT or AST} > 3 \times \text{ULN}$ and $\text{INR} > 1.5$ • Potential Hy's Law cases (defined as $\text{ALT or AST} > 3 \times \text{ULN}$ and $\text{TBL} > 2 \times \text{ULN}$ [mainly conjugated fraction] without notable increase in ALP to $> 2 \times \text{ULN}$) • Any clinical event of jaundice (or equivalent term) • $\text{ALT or AST} > 3 \times \text{ULN}$ accompanied by (general) malaise, fatigue, abdominal pain, nausea, or vomiting, or rash with eosinophilia • Any adverse event potentially indicative of a liver toxicity *

Table 14-2 Follow Up Requirements for Liver Events and Laboratory Triggers

Criteria	Actions required	Follow-up monitoring
Potential Hy's Law case ^a	
 • Discontinue the study drug immediately • Hospitalize, if clinically appropriate • Establish causality • Complete liver CRF 	ALT, AST, TBL, Alb, PT/INR, ALP and GGT until resolution ^c (frequency at Investigator discretion)
ALT or AST > 8 × ULN	
 • Discontinue the study drug immediately • Hospitalize if clinically appropriate • Establish causality • Complete liver CRF 	ALT, AST, TBL, Alb, PT/INR, ALP and γGT until resolution ^c (frequency at Investigator discretion)
> 3 × ULN and INR > 1.5	
 • Discontinue the study drug immediately • Hospitalize, if clinically appropriate • Establish causality • Complete liver CRF 	ALT, AST, TBL, Alb, PT/INR, ALP and γGT until resolution ^c (frequency at Investigator discretion)
> 5 to ≤ 8 × ULN	
 • Repeat LFT within 48 hours • If elevation persists, continue follow- 	ALT, AST, TBL, Alb, PT/INR, ALP and γGT until resolution ^c (frequency

Criteria	Actions required	Follow-up monitoring
	
 up monitoring • If elevation persists for more than 2 weeks, discontinue the study drug • Establish causality • Complete liver CRF 	at Investigator discretion)
> 3 × ULN accompanied by symptoms ^b	
 • Discontinue the study drug immediately • Hospitalize if clinically appropriate • Establish causality • Complete liver CRF 	ALT, AST, TBL, Alb, PT/INR, ALP and γGT until resolution ^c (frequency at Investigator discretion)
> 3 to ≤ 5 × ULN (patient is asymptomatic)	
 • Repeat LFT within the next week • If elevation is confirmed, initiate close observation of the patient 	Investigator discretion Monitor LFT within 1 to 4 weeks
ALP (isolated)		
> 2 × ULN (in the absence of known bone pathology)	
 • Repeat LFT within 48 hours • If elevation persists, establish causality • Complete liver CRF 	Investigator discretion Monitor LFT within 1 to 4 weeks or at next visit
TBL (isolated)		
> 2 × ULN (in the absence of known Gilbert syndrome)	
 • Repeat LFT within 48 hours • If elevation persists, discontinue the study drug immediately • Hospitalize if clinically appropriate • Establish causality • Complete liver CRF 	ALT, AST, TBL, Alb, PT/INR, ALP and γGT until resolution ^c (frequency at Investigator discretion) Test for hemolysis (e.g., reticulocytes, haptoglobin, unconjugated [indirect] bilirubin)
> 1.5 to ≤ 2 × ULN (patient is asymptomatic)	
 • Repeat LFT within the next week • If elevation is confirmed, initiate close observation of the patient 	Investigator discretion Monitor LFT within 1 to 4 weeks or at next visit
Jaundice	
 • Discontinue the study drug immediately • Hospitalize the patient • Establish causality • Complete liver CRF 	ALT, AST, TBL, Alb, PT/INR, ALP and γGT until resolution ^c (frequency at Investigator discretion)

Criteria	Actions required	Follow-up monitoring
Any AE potentially indicative of a liver toxicity*	
Consider study drug interruption or discontinuationHospitalization if clinically appropriateEstablish causalityComplete liver CRF	Investigator discretion

*These events cover the following: hepatic failure, fibrosis and cirrhosis, and other liver damage-related conditions; the non-infectious hepatitis; the benign, malignant and unspecified liver neoplasms

^aElevated ALT/AST > 3 × ULN and TBL > 2 × ULN but without notable increase in ALP to > 2 × ULN

^b(General) malaise, fatigue, abdominal pain, nausea, or vomiting, or rash with eosinophilia

^cResolution is defined as an outcome of one of the following: (1) return to baseline values, (2) stable values at three subsequent monitoring visits at least 2 weeks apart, (3) remain at elevated level after a maximum of 6 months, (4) liver transplantation, and (5) death.

15 Appendix 3: Specific Renal Alert Criteria and Actions

Table 15-1 Specific Renal Alert Criteria and Actions

Serum Event	
Serum creatinine increase 25 – 49% compared to baseline and is above ULN	Confirm 25% increase after 24-48h Follow up within 2-5 days
Acute Kidney Injury: Serum creatinine increase ≥ 50% compared to baseline and is above the ULN	Follow up within 24-48h if possible Consider study treatment interruption Consider patient hospitalization /specialized treatment
Urine Event	
New dipstick proteinuria ≥1+ Albumin- or Protein-creatinine ratio increase ≥ 2-fold Albumin-creatinine ratio (ACR) ≥ 30 mg/g or ≥ 3 mg/mmol; Protein-creatinine ratio (PCR) ≥ 150 mg/g or > 15 mg/mmol	Confirm value after 24-48h Perform urine microscopy Consider study treatment interruption / or discontinuation
New dipstick glycosuria ≥ 1+ not due to diabetes	Blood glucose (fasting) Perform serum creatinine, ACR
New dipstick hematuria ≥ 1+ not due to trauma	Urine sediment microscopy Perform serum creatinine, ACR
For all renal events:	

Document contributing factors in the CRF: co-medication, other co-morbid conditions, and additional diagnostic procedures performed
 
Monitor patient regularly (frequency at investigator's discretion) until either:
 
Event resolution: sCr within 10% of baseline or protein-creatinine ratio within 50% of baseline, or
 
Event stabilization: sCr level with ±10% variability over last 6 months or protein-creatinine ratio stabilization at a new level with ± 50% variability over last 6 months.
	

16 Appendix 4: Weight ranges: recommended maximum sample blood volume per blood draw

Recommended maximum blood collections are in accordance with the 2008 EU Commission Guideline on Ethical Considerations for Clinical Trials on Medicinal Products Conducted with the Pediatric Population. As per the guideline, collections specified in the protocol do not exceed 3% of patients' total blood volume during a 4-week period and/or 1% at any single visit. Patients' total blood volume is estimated at 80 to 90 mL/kg body weight; 3% is 2.4 mL blood per kg body weight, 1% is 0.8 mL blood per kg body weight. The table below outlines the maximum allowable blood volume by weight category. In order to stay within these limits, detailed instructions are provided by the Central Laboratory for all weight categories less than 38 kg.

Table 16-1 Weight range: Recommended maximum blood volume drawn per visit, and per 4 week period

Weight Range Category (kg)	Maximum Allowable Blood Volume Drawn / visit (mL)	Maximum Allowable Blood Volume Drawn / 4 week period (mL)
7-10	5.6	16.8
>10-12	8.0	24.0
>12-14	9.6	28.8
>14-26	11.2	33.6
>26-38	20.8	62.4
>38	30.4	91.2

17 Appendix 5: Physician's global assessment of disease activity (VAS)

The question text below will be shown to and will be answered by the physician. The physician's assessment should be made and recorded without viewing ANY of the patient's assessments. The result of the physician's assessment of the patient's disease activity should be withheld from the patient / parents/guardian so as not to influence his/her own assessment.

The following is the text of the question, but does not represent the final formatting used in the study.

“Considering all the ways ERA/JPsA affects your patient, how would you rate his or her condition today?”

No disease activity	Very severe disease activity
0	100

18 Appendix 6: Childhood Health Assessment Questionnaire (CHAQ)

The following does not represent the final formatting of the CHAQ used in the study.

CHILDHOOD HEALTH ASSESSMENT QUESTIONNAIRE					
1					
2	
In this section we are interested in learning how your child's illness affects his/her ability to function in daily life. Please feel free to add any comments on the back of this page. In the following questions, please check the one response which best describes your child's usual activities (averaged over an entire day) OVER THE PAST WEEK, ONLY NOTE THOSE DIFFICULTIES OR LIMITATIONS WHICH ARE DUE TO ILLNESS. If most children at your child's age are not expected to do a certain activity, please mark it as "Not Applicable". For example, if your child has difficulty in doing a certain activity or is unable to do it because he/she is too young but not because he/she is RESTRICTED BY ILLNESS, please mark it as "NOT Applicable".
				
3	Without ANY Difficulty	With SOME Difficulty	With MUCH Difficulty	UNABLE To do	Not Applicable
4	DRESSING & GROOMING				
5	Is your child able to:				
6	- Dress, including tying shoelaces and doing buttons? 				
7	- Shampoo his/her hair? 				
8	- Remove socks? 				
9	- Cut fingernails? 				
10	ARISING				
11	Is your child able to:				
12	- Stand up from a low chair or floor? 				
13	- Get in and out of bed or stand up in a crib? 				
14	EATING				
15	Is your child able to:				
16	- Cut his/her own meat? 				
17	- Lift up a cup or glass to mouth? 				
18	- Open a new cereal box? 				
19	WALKING				
20	Is your child able to:				
21	- Walk outdoors on flat ground? 				
22	- Climb up five steps? 				
23	* Please check any AIDS or DEVICES that your child usually uses for any of the above activities:				
24	 - Devices used for dressing (button hook, zipper pull, long-handled shoe horn, etc.)   - Built up pencil or special utensils   - Special or built up chair   - Other (Specify: _____) 				
25					
26					
27					
28	* Please check any categories for which your child usually needs help from another person BECAUSE OF ILLNESS:				
29	 - Eating   - Walking 				
30					

	Without ANY Difficulty	With SOME Difficulty	With MUCH Difficulty	UNABLE To do	Not Applicable
31					
